8.15 Serious Adverse Events

An SAE is an AE that:

- Results in death.
- Is life-threatening (see below).
- Requires hospitalization or prolongation of an existing hospitalization (see below).
- Results in a persistent or significant disability or incapacity (see below).
- Results in a congenital anomaly or birth defect.
- Additionally, important medical events that may not result in death, be life-threatening, or require hospitalization may be considered SAEs when, based on appropriate medical judgment, the event may jeopardize the subject and may require medical or surgical intervention to prevent any one of the outcomes listed above in this definition. Examples of such events include allergic bronchospasm requiring intensive treatment in an emergency room or at home, blood dyscrasias or convulsions that do not result in hospitalization, or development of drug dependency or drug abuse.

An AE is considered “life-threatening” if, in the view of the investigator or sponsor, its occurrence places the subject at immediate risk of death. It does not include an AE that, had it occurred in a more severe form, might have caused death. For example, hepatitis that resolved without evidence of hepatic failure would not be considered life-threatening, even though hepatitis of a more severe nature can be fatal. Similarly, an allergic reaction resulting in angioedema of the face would not be life-threatening, even though angioedema of the larynx, allergic bronchospasm, or anaphylaxis can be fatal.

Hospitalization is official admission to a hospital. Hospitalization or prolongation of a hospitalization constitutes criteria for an AE to be serious; however, it is not in itself considered an SAE. In the absence of an AE, a hospitalization or prolongation of a hospitalization should not be reported as an SAE by the participating investigator. This is the case in the following situations:

- The hospitalization or prolongation of hospitalization is needed for a procedure required by the protocol.
- The hospitalization or prolongation of hospitalization is part of a routine procedure followed by the center (eg, stent removal after surgery). This should be recorded in the study file.
- A hospitalization for a preexisting condition that has not worsened.

Disability is defined as a substantial disruption in a person’s ability to conduct normal life functions.

If there is any doubt about whether the information constitutes an SAE, the information is treated as an SAE.

8.16 Other Reportable Information

Certain information, although not considered an SAE, must be recorded, reported, and followed up as indicated for an SAE. This includes:

- Pregnancy exposure to a test article: If a pregnancy is confirmed, use of the test article must be discontinued immediately. Information about pregnancy exposure includes the entire course of pregnancy and delivery, and perinatal and neonatal outcomes, even if there are no abnormal findings. Both maternal and paternal exposures are considered other reportable information. For exposure involving the female partner of a male subject, the necessary information must be collected from the subject, while respecting the confidentiality of the partner.
- Lactation exposure to a test article with or without an AE.
- Overdose of a test article as specified in this protocol with or without an AE.
- Inadvertent or accidental exposure to a test article with or without an AE.

8.17 Overdose

Any administration of omadacycline of greater than 600 mg within a 24-hour period will be an overdose, regardless of whether the overdose is intentional or accidental. It is a reportable event and the sponsor must be notified within 1 business day.

The physician managing the overdose may order any test he/she thinks is necessary to manage the subject properly.

8.18 Medication Errors

Medication errors are the result of administration or consumption of the wrong product, by the wrong subject, at the wrong time, and/or by the wrong administration route, due to human error.

Medication errors include, but are not limited to, the following:

- The administration and/or consumption of test article that has not been assigned to the subject
- Administration of expired test article

All AEs and SAEs must be handled as specified in this protocol whether or not they are associated with a medication error. A medication error associated with an SAE (including overdose, inadvertent exposure, and/or accidental exposure) will be reported with the SAE on the SAE Report Form. All other medication errors will be reported by e-mailing the Clinical Test Article Error Incident Report Form to [contact].

8.19 Recording and Reporting

A subject's AEs and SAEs will be recorded and reported from the signing of the ICF to the time of the Follow-up assessment. The investigator must instruct the subject to report AEs and SAEs during this time period. Reports of death after the last study contact with the subject will be reported to the sponsor and additional information relative to the cause of death will be sought and documented.

All AEs and SAEs must be recorded on source documents. All AEs and SAEs for subjects who receive a treatment assignment will be recorded in the eCRFs.

The investigator must follow up as medically necessary on all AEs and SAEs until the events have subsided, the condition has returned to Baseline, or in case of permanent impairment, until the condition stabilizes.

Adverse events should be based on the signs or symptoms detected during the physical examination and on clinical evaluation of the subject. In addition to the information obtained from those sources, the subject should be asked the following nonspecific question: "How have you been feeling since your last visit?" Whenever possible, AEs should be reported as a diagnosis rather than individual signs and symptoms. If a definitive diagnosis is not possible, the individual signs and symptoms should be recorded using standard medical terminology.

If an AE requires a surgical or diagnostic procedure, the illness leading to the procedure should be recorded as the AE, not the procedure itself.

Death should be recorded in the eCRF as an outcome of an AE. Any unanticipated risks to the subjects must be reported promptly to the IRB/IEC/REB.

8.19.1 Serious Adverse Event Reporting

All SAEs and follow-up information must be reported within 1 business day or 24 hours as required by local regulations by emailing a completed SAE Report to the email address below.

E-Mail: [REDACTED]

8.19.2 Assessment of Relatedness

The investigator will assess causality (ie, whether there is a reasonable possibility that test article caused the event) for all AEs and SAEs. The relationship will be characterized using the following classification:

- Not Related: This relationship suggests that there is no association between test article and the reported event. The event can be explained by other factors such as an underlying medical condition, concomitant therapy, or accident, and no plausible temporal or biologic relationship exists between test article and the event.
- Related: This relationship suggests that a definite causal relationship exists between test article administration and the AE, or there is a reasonable possibility that the

event was caused by the test article, and other conditions (concurrent illness, progression/expression of disease state, or concurrent medication reaction) do not appear to explain the event.

Adverse events and SAEs also will be assessed for their potential relationship to the protocol. A protocol-related AE is one that is not related to the test article but is considered by the investigator or the medical monitor (or designee) to be related to the research conditions, ie, related to the fact that a subject is participating in the study. For example, a protocol-related AE may be an untoward event related to a medical procedure required by the protocol.

8.19.3 Assessment of Severity

The severity (or intensity) of an AE will be classified using the following criteria:

- Mild: These events are usually transient, require minimal or no treatment, and do not interfere with the subject's daily activities.
- Moderate: These events result in a low level of inconvenience or concern with the therapeutic measures. Moderate events may cause some interference with normal functioning but pose no significant or permanent risk of harm.
- Severe: These events interrupt a subject's usual daily activity and may require systemic drug therapy or other treatment. Severe events are usually incapacitating.

Changes in the severity of an AE should be documented as a new event to allow an assessment of the duration of the event at each level of intensity to be performed.

8.19.4 Laboratory Findings

Protocol-defined safety laboratory test results will be analyzed as part of specific laboratory safety analyses. Additional laboratory test results at other timepoints may be available to the investigator as part of standard clinical practice. Throughout the study, laboratory-related abnormalities should be recorded as AEs only if considered clinically significant, outside the range of expected values given the subject's Baseline assessments and clinical course, and not known to be part of another AE diagnosis.

8.19.5 Worsening or Progression of Disease Under Study

Worsening or progression of NTM pulmonary disease caused by *Mycobacterium abscessus* including worsening of baseline symptoms, should not be recorded as an AE unless the worsening/progression also meets the criteria for a serious AE (in which case the event also should be reported as an SAE). If worsening or progression of disease under study requires additional antibiotic therapy, subject will be discontinued from test article and this reason for discontinuation will be recorded in the eCRF.

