6.2 Inclusion Criteria

Subjects must meet all of the following criteria at Screening and/or Baseline to be eligible to participate in the study:

1. Written and signed informed consent must be obtained before any protocol-specific assessment is performed.
2. Male and female subjects age 18 years or older.
3. Diagnosed MABC pulmonary disease as per Infectious Diseases Society of America/American Thoracic Society guidelines criteria. Subjects must have:
 - At least 2 of the following NTM-infection symptoms at Screening and Baseline:
 - Chronic cough, coughing up blood (hemoptysis), wheezing, chest pain, frequent throat clearing, phlegm or sputum production, shortness of breath, fatigue, fever, night sweats, poor appetite, and/or weight loss
 - At least 1 positive pulmonary culture for MABC in the 6 months prior to Screening and 1 positive culture at Screening (note: prior culture and screening cultures must be at least 30 days apart).
 - Radiographic evidence of MABC infection via computed tomography (CT) scan of the chest within 3 months prior to Screening with findings consistent with NTM pulmonary disease. If no CT scan obtained within previous 3 months, one should be performed at Screening to confirm eligibility.
4. Based on the clinical assessment of the investigator, guideline-directed antibiotic therapy for treatment of MABC will not be required within the next 3 months, and a delay, in order for the subject to participate in a placebo-controlled clinical trial, is considered reasonable and clinically acceptable.
5. Be able to produce approximately 5 mL of sputum via spontaneous expectoration or be willing to undergo sputum induction to produce approximately 5 mL of sputum for microbiological evaluation.
6. Females must have a negative serum pregnancy test and agree to use a highly effective form of birth control (eg, abstinence, oral contraceptive, intrauterine device, or barrier contraception [eg, condom], tubal ligation, hysterectomy, bilateral oophorectomy, postmenopausal or vasectomized partner) from Screening through study completion. Males (if sexually active) must agree to use a highly effective method of birth control with female partner(s) from Screening through study completion.

7. Able and willing to adhere with the requirements and restrictions of the study.

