8.3 Medical History

The investigator will perform a comprehensive history at the Screening visit. Significant medical history (at any time) and any medical history within the past 6 months including ongoing medical conditions at the time of signing of the ICF will be recorded.

Where possible, diagnoses are to be recorded. Any event or change in the subject's condition or health status occurring after signing the ICF will be reported as an AE.

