8.13 Other Patient-Reported Outcomes and Clinician-Assessed Outcomes

Patient-reported outcomes are being utilized in this study to help understand and assess the subject's health, quality of life or functional status associated with the disease under study and treatment received. The PROs are completed by the subject without interpretation of the subject's response by a clinician or site staff but should be reviewed for completeness and to assess potential AE information.

All PROs described below will be completed the Day 28, Day 56, and Day 84/EOT visits. In addition, the QOL-B, SGRQ, and PROMIS Fatigue will be collected at Day 1/Baseline visit (prior to first dose of test article).

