8.14 Adverse Events

An AE is any untoward, undesired, or unplanned event in the form of signs, symptoms, disease, or laboratory or physiologic observations occurring in a person given a test article or in a clinical study. The event does not need to be causally related to the test article or clinical study. An AE includes, but is not limited to, the following:

- Any clinically significant worsening of a preexisting condition.
- An AE occurring from overdose of a test article, whether accidental or intentional. Overdose is a dose greater than that specified in the protocol.
- An AE occurring from abuse (eg, use for nonclinical reasons) of a test article.
- An AE that has been associated with the discontinuation of the use of a test article.

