13.4 Vital Signs

Vital signs (systolic blood pressure, diastolic blood pressure, heart rate, pulse oximetry, and temperature) and weight will be summarized using descriptive statistics at baseline and at each post-baseline time point (the Day 28, 58 and 84 visit and Day 84/EOT) as well as for the most extreme result (high and low). Changes from baseline will also be summarized.

Incidence of PCS events will be presented by time point and for the most extreme post-baseline value at any visit (including unscheduled results).

Table 12.4 Vital Sign PCS Thresholds

Criteria for Treatment Emergent PCS Vital Signs

Vital Sign Parameter	Flag	Criterion Value	Change from Baseline
Systolic Blood Pressure (mmHg)	High (CH)	≥ 180	Increase of ≥ 20 mmHg
	Low (CL)	≤ 90	Decrease of ≥ 20 mmHg
Diastolic Blood Pressure (mmHg)	High (CH)	≥ 105	Increase of ≥ 15 mmHg
	Low (CL)	≤ 50	Decrease of ≥ 15 mmHg
Heart Rate (bpm)	High (CH)	≥ 120	Increase of ≥ 15 bpm
	Low (CL)	≤ 50	Decrease of ≥ 15 bpm
Temperature (°C)	Low (CL)	<36.0	NA
	High (CH)	>38.0	NA

bpm=beats per minute; C=Celsius; DBP=diastolic blood pressure; SBP=systolic blood pressure

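### Protocol 8.19.5 exempts non-serious worsening of baseline symptoms from AE recording without asking about drug cause, and it is not reconciled with 8.3 and 8.14

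*Protocol*

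**What the plan says.** Three protocol sections govern whether a post-consent change becomes an AE.

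- **8.14 (Adverse Events)** lists "Any clinically significant worsening of a preexisting condition" among AEs and adds that "The event does not need to be causally related to the test article or clinical study". It makes no exception for the disease under study.
- **8.3 (Medical History)** states: "Any event or change in the subject's condition or health status occurring after signing the ICF will be reported as an AE". It makes no exception either.
- **8.19.5** takes as its subject worsening or progression of the NTM lung disease itself, "including worsening of baseline symptoms, should not be recorded as an AE unless the worsening/progression also meets the criteria for a serious AE". If worsening calls for additional antibiotics, the subject stops test article and that reason goes into the eCRF.

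The symptoms concerned are those of Protocol 6.2, inclusion criterion 3, which requires "At least 2 of the following NTM-infection symptoms at Screening and Baseline". The list runs "Chronic cough, coughing up blood (hemoptysis), wheezing, chest pain, frequent throat clearing, phlegm or sputum production, shortness of breath, fatigue, fever, night sweats, poor appetite", with weight loss as the twelfth item.

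Protocol 8.19.2 has the investigator rate causality for AEs and SAEs. SAP 13.2 builds every AE summary from TEAEs reported in the eCRF.

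**The concern.** AE incidence is the first endpoint under the primary safety objective (Protocol Section 4). Protocol 3.2 describes this as the first trial to dose omadacycline beyond 14 days, and there is no data monitoring committee (Protocol 12.7). The TEAE tables therefore carry most of the tolerability evidence for the new length of exposure.

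Several listed symptoms could worsen through drug intolerance as well as through disease. A subject who already has one at baseline falls under 8.19.5 if that symptom worsens without becoming serious. Read literally, the section removes the event before anyone rates its cause. Another site, following 8.14 or 8.3 in equally good faith, records the same event with causality, severity and action taken. At stake are consistent recording across about 20 sites and complete relatedness and discontinuation tables.

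**Working it through.** The point rests on no design figure, so the check is a comparison of texts. Take one case: mild poor appetite at baseline becomes severe on treatment and is not serious.

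| Rule | Recorded as an AE? |
|---|---|
| 8.14, general definition | Yes if clinically significant, whatever the cause |
| 8.3, change after consent | Yes |
| 8.19.5, read literally (baseline symptom, not serious) | No |
| 8.19.5, read as covering disease worsening only | Depends on attribution, for which the section gives no test |

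**Do the sections refer to each other?** No. Neither 8.3 nor 8.14 points to 8.19.5, and 8.19.5 does not say that it overrides them.

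**Could a later step recover the event?** The protocol has a suitable tool. The definition of a related event in 8.19.2 asks whether other conditions, including disease progression, appear to explain it. But 8.19.2 applies only once an event is an AE or SAE, and 8.19.5 acts before that. Protocol 8.13 says that the other patient-reported outcomes "should be reviewed for completeness and to assess potential AE information", yet a worsened baseline symptom found in that review meets the same exemption.

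**Which outputs lose the event?** All that SAP 13.2 builds from TEAEs: incidence by system organ class and preferred term, highest severity, relationship, test article discontinuation, and the split at Day 15 that isolates the longer exposure.

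**What still shows part of it?**

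- SAP 12.2.8 gives shift tables by symptom and visit. They are an efficacy output in the ITT set and carry no causality or action taken.
- SAP 13.4 summarizes weight and pulse oximetry by visit, as change from baseline and as the most extreme result.
- Protocol 8.21 lists AE and worsening of the disease as separate reasons for discontinuation. A stop coded to the second reason need not appear among TEAEs leading to discontinuation.
- Serious worsening remains recordable, and 8.19.5 does not exempt symptoms absent at baseline.

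**Size.** The number of events left out depends on three quantities: the rate of non-serious worsening related to test article, the share occurring in a symptom already present, and the share of sites that apply the exemption to it. The documents give none of them. The loss could be zero, if every site confines 8.19.5 to disease worsening, or could include all such events, if every site applies it literally.

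**The case against.** The strongest reply is that the full sentence in 8.19.5 concerns worsening of the disease, with baseline symptoms as an instance of it. A specific section commonly narrows a general definition, and 8.19.4 does so for laboratory findings. Symptom worsening is also an efficacy measure (response Definition 2), so keeping it out of the AE tables is a legitimate choice. An investigator who blames the drug could still record an AE and select AE as the reason for stopping. This reading is reasonable, and it limits the point to what can happen. It does not remove the point, because the protocol nowhere states that reading and gives no rule for doubtful attribution.

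A reader might infer four stronger things that the documents do not support.

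- **Worsening goes unseen for most of the treatment period.** The symptom questionnaire has a 7-day recall at three post-baseline visits (3 × 7 = 21 of 84 days). Only worsening that starts and resolves wholly between recall periods would escape it. Sustained worsening would be reported at a visit, and measured weight does not depend on recall.
- **A definite number of omadacycline subjects is missing.** No rate is given, and the documents do not say that omadacycline causes these symptoms.
- **The comparison is biased in the drug's favor.** The exemption applies to both arms. If the drug works, placebo subjects may have more exempted disease worsening.
- **Objective signs are not analyzed.** The table headed "Criteria for Treatment Emergent PCS Vital Signs" has no row for weight or pulse oximetry, but SAP 13.4 summarizes both, including extreme values. Threshold rows are a separate matter.

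**Conclusion.** The concern holds as a gap in the recording rule. Protocol 8.3, 8.14 and 8.19.5 give different answers for non-serious worsening of a baseline symptom, and 8.19.5 does not say how to record worsening that test article may have caused. Such events can be recorded differently by site and can be missing from the TEAE, relatedness and TEAE-discontinuation tables. The other displays show only part of the picture, without a causality rating.

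The size and net direction of any effect on the comparison with placebo are unknown. The conclusion assumes that some sites could read 8.19.5 literally, and that some listed symptoms can worsen for reasons other than the infection. It does not assume that omadacycline is known to cause them. Because the outcome affected is a primary safety endpoint and the correction is mainly wording, the sections should be reconciled.

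**What to change.** Reconcile 8.3, 8.14 and 8.19.5 with explicit cross-references. Limit the 8.19.5 exemption to non-serious worsening that the investigator judges not related to test article. Worsening with a reasonable possibility of relation, by the standard already in 8.19.2, would then be recorded as an AE with causality, severity and action taken. Disease worsening without such a possibility stays exempt, which preserves the purpose of 8.19.5.

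The supplied SAP is version 5.0, signed in September 2024, so data collection may have ended. In that case, state in the CSR which rule sites applied. Present the shift tables for baseline symptoms beside the TEAE tables as a safety display, preferably in the safety analysis set. This cannot supply causality ratings that were never made.

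The cost is protocol wording, site instruction and somewhat more AE records, or, after data collection, one repeated display and a CSR statement. No new assessment is needed. Attribution remains an investigator's judgment and may still vary between sites.

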8.19.6 Pregnancies

To ensure subject safety, each pregnancy in a subject on test article must be reported to the sponsor within 1 business day of learning of its occurrence. Test article should be discontinued immediately, and the pregnancy should be followed up to determine outcome,

including spontaneous or voluntary termination, details of the birth, and the presence or absence of any birth defects, congenital abnormalities, or maternal and/or newborn complications.

Pregnancy should be recorded on a Clinical Trial Pregnancy Form and reported by the investigator to the sponsor. Pregnancy follow-up should be recorded on the same form and should include an assessment of the possible relationship to the test article of any pregnancy outcome. Any SAE experienced during pregnancy must be reported on the SAE Report Form.

